6.3.2.1 Supportive therapy for adverse events suspected of being associated with nivolumab

A list is provided below of examples of supportive therapy to manage adverse events with possible immunological etiology suspected of being associated with nivolumab. For details, refer to the guidance document regarding such events. A dose reduction in steroids can exacerbate symptoms, and, therefore, due care should be paid to the fact that the steroid dose should be gradually decreased over a number of courses. Additional supportive therapy may be required, and, therefore, efforts should be made to exclude other causes of each symptom (e.g., metastatic lesions and bacterial and viral infections).

Pneumonitis:

- In the event of grade 2 pneumonitis, systemic corticosteroids will be administered. When symptoms are returned to below grade 1, the dose of steroids will gradually be decreased over ≥4 weeks.
- In the event of grade 3–4 pneumonitis, steroid therapy will be administered immediately via an intravenous infusion. In addition, anti-inflammatory drugs will be administered as required.
- When steroid therapy is prolonged, antibiotics will be additionally administered to prevent opportunistic infections.

Diarrhea/colitis:

- The presence or absence of signs and symptoms of enteritis (e.g., diarrhea, abdominal pain, blood or mucus in the stool, presence or absence of accompanying fever), as well as signs and symptoms of intestinal perforation (signs of peritonitis and/or intestinal obstruction) will be verified.
- All patients who develop diarrhea/colitis will be instructed to drink sufficient water. If it is difficult for patients to drink adequate water, an intravenous infusion of fluid containing electrolytes will be administered. In the event of ≥grade 2 diarrhea, to confirm or rule out colitis, consultation of a gastroenterologist and endoscopic examination will be recommended.
- In the event of persistent grade 2 diarrhea/colitis lasting ≥3 days, oral corticosteroids will be administered.
- In the event of persistent grade 3–4 diarrhea/colitis lasting ≥1 week, a steroid intravenous infusion, followed by high-dose oral steroids will be given.
- When symptoms are returned to below grade 1, the steroid dose will be gradually decreased over a period of ≥4 weeks.

>Grade 3 hyperglycemia accompanied by type-1 diabetes (including diabetic ketoacidosis in the event of newly developed type-1 diabetes), ketosis (ketonuria), and/or metabolic acidosis:

 For grade 3–4 hyperglycemia accompanied by type-1 diabetes, metabolic acidosis, and/or ketonuria, insulin replacement therapy will be considered. • The serum glucose level and metabolism test values (e.g., urinary ketones, glycohemoglobin, and C-peptides) will be evaluated.

Hypophystitis:

- For grade 2 hypophystitis, corticosteroids will be administered. When symptoms are returned to below grade 1, the steroid dose will be gradually decreased over a period of ≥4 weeks. Because the steroid dose is gradually decreased, appropriate hormone replacement therapy may be needed.
- For grade 3–4 hypophystitis, an intravenous infusion of corticosteroids, followed by oral corticosteroids will be given. When the symptoms return to below grade 1, the steroid dose will be gradually decreased over a period of ≥4 weeks. Because the steroid dose is decreased gradually, appropriate hormone replacement therapy may be required.

Hyperthyroidism and hypothyroidism:

Thyroid dysfunction can occur at any time during the dose administration. Changes in thyroid function test values (conducted at the start of investigational drug dosing, then as subsequently required according to routine and clinical evaluations), as well as the presence or absence of signs/symptoms of thyroid dysfunction should be monitored.

- Grade 2 hyperthyroidism (and grade 3–4 hypothyroidism):
 - In hyperthyroidism, nonselective beta-blockers (e.g., propranolol) are recommended as the first line of treatment.
 - In hypothyroidism, thyroid hormone replacement therapy (e.g., levothyroxine or liothyronine) are recommended as standard treatment.
- Grade 3–4 hyperthyroidism:

Following the intravenous infusion of corticosteroids, oral corticosteroids will be administered. When symptoms return to below grade 1, the steroid dose will be gradually decreased over a period of ≥ 4 weeks. Because the steroid dose is decreased gradually, appropriate hormone replacement therapy may be required.

Liver impairment:

- For grade 2 liver impairment, liver function tests will be performed frequently until the baseline values are restored (performance of weekly tests will be considered).
- 1) Corticosteroids will be administered via an intravenous infusion or orally.
- For grade 3–4 liver impairment, corticosteroid therapy will be administered for 24–48 h via an intravenous infusion.
- When symptoms are returned to below grade 1, the steroid dose will be gradually decreased over a period of ≥4 weeks.

Renal impairment and nephritis:

• For grade 2 impairment, corticosteroid therapy will be administered.

- For grade 3-4 impairment, corticosteroid therapy will be administered.
- When the symptoms return to below grade 1, the steroid dose will be gradually decreased over a period of ≥4 weeks.

Infusion reaction management: The signs and symptoms of an infusion reaction normally appear during administration of the drug or immediately after administration, and most patients completely recover within 24 h of administration.

Table 8 lists the countermeasures to take in the event that an infusion reaction associated with nivolumab occurs.

For grade 2 or grade 3-4 immunity-related toxicities (other than those listed above), systemic corticosteroid therapy will be administered as required upon deliberation with the trial coordinating committee. When symptoms are returned to below grade 1, the steroid dose will be gradually decreased over a period of \geq 4 weeks.

| NCI-CTCAE grade | Countermeasures | Pretreatment upon the |
|------------------------------|---|------------------------|
| | | administration of the |
| | | next and subsequent |
| | | doses |
| Grade 1 | Increase the frequency of monitoring of | None |
| Mild reaction; does not | vital signs until the symptoms of the | |
| require infusion suspension | patient concerned are deemed stable by | |
| or treatment. | the attending physician. | |
| Grade 2 | Suspend nivolumab dosing and monitor | 1.5 h (±30 min) before |
| Infusion suspension is | symptoms. | nivolumab dosing. |
| needed; however, the | Administer appropriate treatment (e.g., | administer |
| subject responds instantly | intravenous transfusion, anti-histamines, | pretreatment with the |
| to symptomatic treatment | NSAIDs, acetaminophen, and opioid | drugs below. |
| (e.g., anti-histamines, | analgesics). | |
| nonsteroidal | Increase the frequency of monitoring of | Oral diphenhydramine |
| anti-inflammatory drugs | vital signs until the symptoms of the | at a dose of 50 mg (or |
| (NSAIDs), opioid | patient concerned are deemed stable by | similar |
| analgesics, and intravenous | the attending physician. | antihistamine). |
| transfusion); prophylactic | If the subject recovers from symptoms | |
| treatment is required within | within 1 h of dose suspension, dosing is | Oral acetaminophen at |
| 24 h. | resumed at an infusion rate of 50% of the | a dose of 500-1000 |

Table 7: Countermeasures in the event of an infusion reaction associated with nivolumab

| | initial rate (e.g. 50 mI /h from 100 mI /h) | mg (or a similar | | | | | | |
|-------------------------------|---|------------------------|--|--|--|--|--|--|
| | If the subject does not receiver from | antifabrila agant) | | | | | | |
| | | antifeorne agent). | | | | | | |
| | symptoms within 1 h of dosing | | | | | | | |
| | suspension, the dose will be withdrawn | | | | | | | |
| | until the symptoms recover, and | | | | | | | |
| | pretreatment will be administered at the | | | | | | | |
| | time of the next dose. | | | | | | | |
| | In patients who develop ≥grade 2 | | | | | | | |
| | toxicities despite appropriate pretreatment, | | | | | | | |
| | nivolumab treatment will be terminated | | | | | | | |
| | (no resumption of dosing permitted). | | | | | | | |
| Grade 3 | Suspend nivolumab dosing and monitor | Nivolumab dosing is | | | | | | |
| Prolongation (the subject | symptoms. | not resumed. | | | | | | |
| does not respond quickly to | Administer appropriate treatment (e.g., | | | | | | | |
| symptomatic treatment and | intravenous transfusion, anti-histamines, | | | | | | | |
| short-term infusion | NSAIDs, acetaminophen, opioid | | | | | | | |
| suspension); recurrence | analgesics, oxygen inhalation, | | | | | | | |
| despite improving once; | hypertensive drugs, corticosteroids, and | | | | | | | |
| hospital admission is | epinephrine). | | | | | | | |
| required for sequelae (e.g., | Increase the frequency of monitoring of | | | | | | | |
| renal impairment, | vital signs until the symptoms of the | | | | | | | |
| pulmonary infiltration). | patient concerned are deemed stable by | | | | | | | |
| | the attending physician. The patient is | | | | | | | |
| Grade 4 | hospitalized as required. | | | | | | | |
| Life-threatening; | Nivolumab treatment is terminated (no | | | | | | | |
| administration of | resumption of dosing permitted). | | | | | | | |
| hypertensive drugs and | | | | | | | | |
| artificial respiration is | | | | | | | | |
| needed. | | | | | | | | |
| During nivolumab dosing, ap | ppropriate resuscitation equipment is placed in | n the room so that the | | | | | | |
| physician can respond quickly | physician can respond quickly. | | | | | | | |

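### The written steroid start for diarrhea/colitis runs against severity: 3 days for grade 2, but 1 week for grade 3–4

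*Combined protocol and SAP*

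**What the plan says.** Section 6.3.2 sends investigators to two places for supportive therapy, corticosteroids included: section 6.3.2.1 and the management algorithms in an appendix of the investigator brochure. Section 6.3.2.1 introduces its content as follows: "A list is provided below of examples of supportive therapy to manage adverse events". It refers to a guidance document for details.

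The diarrhea/colitis entry has two steroid lines:

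- Grade 2: "In the event of persistent grade 2 diarrhea/colitis lasting ≥3 days, oral corticosteroids will be administered".
- Grade 3–4, again if persistent: "lasting ≥1 week, a steroid intravenous infusion, followed by high-dose oral steroids will be given".

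The grade 3–4 steroid instructions for other toxicities in the same section read:

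- Pneumonitis: "steroid therapy will be administered immediately via an intravenous infusion".
- Hypophysitis: "an intravenous infusion of corticosteroids, followed by oral corticosteroids will be given".
- Hyperthyroidism: "Following the intravenous infusion of corticosteroids, oral corticosteroids will be administered".
- Liver impairment: "corticosteroid therapy will be administered for 24–48 h via an intravenous infusion".
- Renal impairment and nephritis: "For grade 3-4 impairment, corticosteroid therapy will be administered".

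Table 7, in the same section, includes corticosteroids among the countermeasures for grade 3–4 infusion reactions. A closing catch-all gives steroids as needed for other immune toxicities of grade 2 or grade 3–4, after discussion with the coordinating committee.

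**The concern.** A steroid trigger would be expected to come no later as severity rises. Here it comes later. A site that follows the entry as written starts oral steroids at 3 days in grade 2 colitis and waits a week in grade 3–4.

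Section 2.5.2 names colitis among the main immune toxicities of nivolumab, so the line will be consulted. One or two further institutions are planned for the expansion cohort, and section 13.4.1 bars sites from altering the protocol themselves. The correction therefore has to come from the coordinating committee.

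Patient safety is the main issue. There is a secondary link to the primary endpoint: two DLT clauses in section 6.1.3 depend on how a severe event behaves under steroids or supportive care, so the time at which steroids start is not wholly separate from DLT counting.

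**Working it through.** The plan gives no figure to reproduce. The check is a comparison of written rules plus simple subtraction.

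**Step 1. The two thresholds (section 6.3.2.1).** Grade 2: at least 3 days. Grade 3–4: at least 1 week, that is 7 days. Difference: 7 − 3 = 4 days longer for the more severe grade.

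**Step 2. Comparison across the section.** The liver steroid line is read as belonging to grade 2, because it follows that bullet.

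| Toxicity | Steroid wait, grade 2 | Steroid wait, grade 3–4 |
|---|---|---|
| Pneumonitis | none stated | immediate |
| Diarrhea/colitis | 3 days | 7 days |
| Hypophysitis | none stated | none stated |
| Hyperthyroidism | no steroid line (beta-blocker) | none stated |
| Liver impairment | none stated | none stated |
| Renal impairment/nephritis | none stated | none stated |
| Infusion reaction (Table 7) | steroids not listed | none stated |
| Catch-all, other immune toxicity | as needed | as needed |

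At grade 3–4, 1 of 7 named toxicities states a wait (1 of 8 with the catch-all). Five named toxicities have steroids at both grades, six with the catch-all. In only one of these is the severe-grade wait the longer one. Type 1 diabetes/hyperglycemia is left out because its line concerns insulin.

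**Step 3. Search for an earlier start elsewhere.** Section 6.5.1 recommends steroids for immune-related events, and section 6.5.3 exempts such use from its prohibition. Neither gives a grade or a start time. The opening of section 6 lets the investigator change treatment in a medical emergency. No supplied text sets an explicit earlier start for grade 3–4 diarrhea/colitis.

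**Step 4. Link to DLTs (section 6.1.3, 28-day window).** Two conditional clauses matter. Both also require the investigator to judge that treatment cannot continue even with supportive therapy.

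- *Diarrhea of grade 3 or more for at least 5 consecutive days.* This duration is reached 7 − 5 = 2 days before the written steroid trigger.
- *Immune-related event of grade 3 or more lasting more than 8 days even after steroids.* The text does not say from when the 8 days run.
  - Counted from steroid start: a day-7 start puts the threshold at 7 + 8 = 15 days after onset, so onset must fall in about the first 28 − 15 = 13 days of the window. A day-3 start gives 3 + 8 = 11, and 28 − 11 = 17 days.
  - Counted from event onset: a day-7 start leaves 8 − 7 = 1 day on steroids before the threshold. A day-3 start leaves 8 − 3 = 5 days.

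On the first count a late start makes the clause harder to meet inside the window. On the second it leaves steroids less time to prevent the clause being met. The direction of any effect therefore cannot be settled from the documents.

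**The case against.** The strongest reply is that this is one line in a list of examples, and that the operative rule may sit in the guidance document or the brochure algorithm. Neither is in the file, so what sites would actually do is unknown. That stands, and it limits the claim to the written trigger. It does not remove the problem: section 6.3.2 sends sites to this text alongside the brochure, and the line is worded as an instruction. If the outside documents start earlier, the protocol conflicts with them. If they do not, nothing corrects it.

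Second, the two lines trigger different regimens. The grade 3–4 line says when intravenous and high-dose oral treatment is given. It does not say that all steroids are withheld until then, and a patient worsening from persistent grade 2 may already be on oral steroids. That is fair, and it narrows the gap mainly to events that begin at grade 3–4.

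Third, regorafenib itself causes diarrhea (section 2.6.2: 34.7% overall, 5.9% at grade 3 or higher), and section 6.3.2.1 asks for other causes to be excluded. This can justify requiring persistence before steroids. It cannot justify requiring more persistence at grade 3–4 than at grade 2.

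A reader might go further and infer that severe colitis is left untreated for a week. The documents do not support that. Table 6 withholds nivolumab at grade 2–3 and ends it at grade 4 with no duration condition, and Table 6.3.1.4 interrupts or stops regorafenib at grade 3 or 4. Fluids, the perforation check and the endoscopy recommendation are not delayed, and earlier steroids are allowed.

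A reader might also infer that DLTs will be miscounted. That is not shown either. Missing one nivolumab dose because of toxicity in the window is itself a DLT under section 6.1.3, so some of these events would be captured regardless.

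**Conclusion.** The point holds for the written trigger. The diarrhea/colitis entry in section 6.3.2.1 places the steroid start in reverse order of severity, by 4 days. It is the only one of seven named toxicities treated with steroids at grade 3–4 that states a wait at that grade. This is a stated rule in the wrong order rather than missing detail, and it should be fixed.

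The conclusion assumes that the supplied text is what sites read and that the unseen documents do not override it. The documents give no rate of grade 3–4 immune colitis lasting a week, so no frequency of harm is estimated. They do not show whether the 1-week figure is a drafting or translation slip. An effect on DLT ascertainment cannot be excluded, but its direction and size are unknown.

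It would be tempting to conclude that persistence should be dropped altogether for grade 3–4. The documents support only a start no later than the grade 2 trigger. An immediate start would have to come from the cited algorithm.

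**What to change.** First compare the line with the management algorithm cited in section 6.3.2. Then reword the grade 3–4 instruction so that intravenous steroids, followed by high-dose oral steroids, begin no later than 3 days into the event. If the algorithm gives an immediate start, remove the wait entirely. No change to the DLT definitions in section 6.1.3 is proposed.

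Under section 13.4.4 a memorandum does not change protocol content, so it is not sufficient. A revision needs approval at each study site, plus IRB approval of the revised document (section 13.4.5). If the coordinating committee judges that the change could increase patient risk or substantially affect the primary endpoint, it becomes an amendment and also needs approval from the efficacy and safety evaluation committee. The possible link to DLT ascertainment should be weighed in that decision.

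The cost is one line of text and the approvals. No patients, procedures or analyses are added.

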6.4 Specific instructions for subjects

The attending physician and trial collaborators will instruct the subjects on the methods of regorafenib and nivolumab administration and on observing the following matters. When

administered on an outpatient basis, a thorough interview and investigation will be carried out regarding the state of regorafenib administration (e.g., the collection of untaken regorafenib [i.e., the investigational drug]), and the results will be recorded on a CRF.

6.5 Combination therapy and supportive treatment

All concomitant drugs and combination therapies used from the beginning of the treatment protocol until 30 days after the final dose (when aftertreatment is administered and up to the day before administration of aftertreatment) will be recorded on a CRF. Drugs used for various tests and diagnoses do not need to be recorded on the CRF, except when required to determine a causal relationship with adverse events or for another reason.

6.5.1 Recommended combination and supportive therapies

The combination and supportive therapies listed below are recommended. Nonadministration of the therapies will not be considered a deviation from the protocol.

- 1) G-CSF will be administered in accordance with the approved usage and dosage.
- Antiemetic agents/fluid replacement: For severe nausea and vomiting that impedes the continuation of oral therapy, the appropriate treatment will be administered using antiemetic agents or fluid replacement.
- 3) Antidiarrheal drugs.
- 4) Antifebrile agent, analgesics, and steroids will be administered for immune-related events.

6.5.2 Permitted combination and supportive therapies

When zoledronic acid and denosumab are administered for bone metastasis before enrollment, such medications can be continued.

6.5.3 Unpermitted combination and supportive therapies

During the study, strong CYP3A4 inhibitors (eg, clarithromycin, grapefruit juice, indinavir, itraconazole, ketoconazole, nefazodone, nelfinavir, posaconazole, ritonavir, saquinavir, telithromycin, voriconazole) or strong CYP3A4 inducers (eg, carbamazepine, phenobarbital, phenytoin, rifampin, St. John's Wort) are not permitted (See appendix 3).

Except when required for the treatment of adverse events, safety, and ethical reasons, the concurrent use of the agents listed below shall not be permitted.

- 1) Other anticancer drugs
- 2) Other investigational drugs

3) Live vaccines administered <30 days before the initiation of treatment with the investigational drug and during the trial period. Examples of live vaccines are as follows (however, the list is not exhaustive): measles, mumps, rubella, chicken pox/herpes zoster, yellow fever, rabies*, BCG for

tuberculosis, and typhoid vaccines*. Inoculation with inactive vaccines (e.g., seasonal influenza vaccines) is permitted; however, the intranasal administration of attenuated influenza vaccines (e.g., Flu-Mist®) is prohibited. (*In Japan, live vaccines are not approved).

4) Systemic glucocorticoids for purposes other than treating symptoms caused by notable events with a suspected immunological etiology. Upon deliberation with the trial coordinating committee, the use of corticosteroids may be permitted according to the physiological dose required to alleviate symptoms (e.g., to control symptoms of acute asthma).

Except when required for the treatment of adverse events, safety, and ethical reasons, the concurrent use of the drugs listed below is not permitted. However, use of these drugs to treat adverse events will not be considered a deviation from the protocol.

5) Other treatments that affect the evaluation of safety and efficacy (e.g., surgical treatment, radiotherapy, thermotherapy, immunotherapy, hormone therapy, and antibody therapy).

6.6 Aftertreatment

There will be no aftertreatment for subjects following the termination of the stipulated treatment protocol.

7 Investigational drug information

| Investigational drug | Nivolumab |
|-----------------------|--|
| Formulation: | Injection solution |
| Manufacturer: | Ono Pharmaceutical Co., Ltd. |
| Content: | Nivolumab injection solution: 100 mg/10 mL (10 mg/mL) |
| Usage: | Nivolumab injection solution is injected undiluted (10mg/mL) or |
| | diluted with physiological saline or 5% glucose injection solution |
| | to the total injection volume of 160mL or less, and through the |
| | in-line filter with a pore size of 0.2 to $1.2\mu m$. The whole amount is |
| | administered intravenously over 30 minutes (25-40minutes). |
| | However, for subjects weighing less than 40kg, the total injection |
| | volume should not exceed 4mL/kg. After intravenous |
| | administration, flush with a sufficient amount of physiological |
| | saline or 5% glucose solution. After preparation, if not used |
| | immediately, it is possible to save up to 24 h dosing liquid at |
| | refrigeration (2 \sim 8 $^{\circ}$ C.), to store them at room temperature for up |
| | to 8 hours (up to 25 $^{\circ}$ C.) and under room light It is possible. |
| | When storing at room temperature and in room light, use within 8 |
| | hours after preparation, including administration time. |
| | *When administering nivolumab from the CV port or PICC, it is |
| | recommended that the dosage of nivolumab be adjusted so that the |
| | final concentration after dilution is 1.9 mg / mL or more. |
| | * It is recommended that Nivolumab could be dipped in the CV |
| | port or PICC catheterization, and flushing be performed before |
| | administration of the drug through the CV port or PICC. |
| | * When administering nivolumab through the CV port or PICC, |
| | carefully observe the subject's condition during or after |
| | administration. |
| Administration route: | Intravenous infusion |
| Expiration date | Refer to the procedures regarding investigational drug |
| | management |
| Labeling | The outside of the box lists the content, lot number, expiration |
| | date, number of doses, and storage method along with the name, |
| | job title and address of the coordinating physician. The box will |
| | also note that the drug is for use in the trial. |

